Title of project:

Tropical application of low-concentration (0.01%) atropine on the human eye with fast and slow myopia progression rate

Summary

NCT03374306

Date: 1 Jan 2018

Myopia (short-sightedness) has been an epidemic worldwide. In Hong Kong, the prevalence of myopia is approximately 80% at the end of childhood, and the rate of myopia progression among children varies. **Tropical application of 0.01% atropine is a newly recommended pharmacological myopia control treatment.** Recent studies reported that it is effective to slow down myopia progression. **The findings from my GRF 2013 study showed that young children with an initial weakened central electrical signal from the inner retina had faster myopia progression. This indicates that the central retinal electro-activity is an important indicator to find out the predisposed risk of fast myopia progression.** Since the electro-retinal activities measured by my new protocol can classify the children into fast or slow myopia progression group, we speculate that studying the effect of atropine on these two groups will help us better understand the effectiveness of the drug in myopia control for the children with different predisposed risks.

There has been no study investigating the treatment effect of atropine on the children with either fast or slow myopia progression rate, neither has there been clinical finding to demonstrate whether the children with either fast or slow myopia progression will show the same treatment effect of atropine. Hence, longitudinally studying the underlying retinal activities that regulate the control of myopia progression using atropine in these two group of children will help evaluate the clinical effectiveness and improve the clinical judgement in prescribing this treatment.

Our project is a **24-month longitudinal randomized controlled trial that aims to investigate the myopia development after topical application of 0.01% atropine in children with either fast or slow myopia progression classified according to their initial electro-retinal responses. This will help elucidate the effectiveness of using low concentration atropine for myopia control in children with different myopia progression rates.** All of the participated children will be allocated into fast or slow myopia progression group in accordance with the electro-retinal activities as measured by our established protocol from my GRF 2013 study. This protocol also enables us to find out how the retinal electrophysiological changes under the atropine treatment over a 24-month period. The characteristics of these retinal activities will help us to understand the retinal contribution to myopia development in human eye. Furthermore, it will advance our clinical decision to prescribe an appropriate myopia control treatment and be beneficial for the design of a highly effective treatment protocol for myopia control.

Subjects

Based on the study of ATOM2 (Chia et al., 2012), the mean myopia progression rate under 0.01% atropine was -0.49 ± 0.63 D and the mean myopia progression rate in control was -1.20 ± 0.69 D). Hence, 9 subjects should be required for this project to demonstrate the effect of atropine on myopia control (type I error of 5% and the power of 80%; effect size = 1.07, two-tailed; paired group; GPower 3.1). However, based on the mfERG data of our pilot study (Figure 1), the mean inner retinal responses from fast and slow myopia progression group are 67.04 ± 30.54 uV/deg² and 80.61 ± 27.24 uV/deg², therefore the proposed study requires 38 subjects (type I error of 5% and the power of 80%; effect size = 0.47, two-tailed; paired group; GPower 3.1). Assume that the dropout rate of this study throughout the 2-year period is around 5% (according to our preliminary result from my GRF 2013 study) and after consolidation of both analyses, at least 40 subjects aged from 8 to 9 years will be recruited. Children at this age range are believed to be the group with the highest chance of myopia progression. As this study is a randomized controlled trial with two arms, one is the treatment arm and the other one is placebo arm. We will recruit 80 subjects in this study. All of them will receive an ophthalmic assessment including history taking, preliminary tests, objective and subjective refraction, external and internal ocular health assessments. The subjects who meet the following criteria will be recruited to participate in this study. The subjects must have the refractive error between -0.5D and -1D in both eyes and with the best-corrected visual acuity of logMAR 0.00 or better, normal color vision and ocular health. Subjects with any ocular disease, systemic disease and current or history of epilepsy will be excluded from the study.

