Title of Project: Tropical application of low-concentration (0.01%) atropine on the human eye with fast and slow myopia progression rate

NCT03374306

Date: 1 Jan 2018

Statistical analysis

Due to COVID-19-dependent closure of the university campus, the eye examinations were not always performed within the study-defined time window and were in-part delayed. To minimize the effect of delayed visits, change from baseline in SER and AL were normalized for time and expressed as annualized change for each participant. All participants included in the analysis had completed the baseline eye examination and at least 2 visits of follow-up eye examinations during the study period.

The data distribution was approximately normal (Shapiro-Wilk test – SER: $p = 0.16$; AL: $p = 0.27$). A univariate general linear model (GLM) was used to compare annualized change in SER and AL between the treatment groups (atropine vs. placebo), controlling for the baseline SER and age as covariates. Since a weakened central inner retinal response was reported as a risk factor for myopia development, the relationship between Ring 1 IC and annualized change in SER and AL were evaluated using GLM, and compared between the atropine and the placebo groups using moderator analysis. The correlation coefficients (R_p vs. R_a) were also compared between treatment types using Fisher's R-to-Z test in the Ring 1 IC, as well as other regions and MOFO mfERG parameters. All statistical procedures were performed with SPSS22.0 (IBM, Armonk, NY). Hochberg's adjustment was applied for multiple comparisons, with significance level set at $p \leq 0.05$. A receiver operating characteristics analysis was also performed to evaluate the predictive value of baseline Ring 1 IC on fast progressor (annualized progression ≥ 1.0 D) in each of the atropine and control group.

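### Randomisation is not tied to the baseline fast/slow classification that the trial is about, and the main GLM leaves out the baseline retinal response; stratifying and adjusting would bring a modest gain at small cost

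*Protocol*

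**What the plan says.** The protocol's Summary makes the fast/slow comparison the purpose of the trial: "we speculate that studying the effect of atropine on these two groups will help us better understand the effectiveness of the drug". The children are "classified according to their initial electro-retinal responses", so the grouping variable is a baseline measurement, and it applies to everyone: "All of the participated children will be allocated into fast or slow myopia progression group in accordance with the electro-retinal activities".

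The Subjects section describes the allocation only in these terms: "As this study is a randomized controlled trial with two arms, one is the treatment arm and the other one is placebo arm". It then says "We will recruit 80 subjects in this study". It gives no allocation ratio, sequence method, blocking or stratification factor, and no order for classification and randomisation. No cut-off separating fast from slow is stated, and no expected share of fast children.

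The SAP's Statistical analysis section compares annualised change in SER and AL between arms with a GLM whose covariates are baseline SER and age. Ring 1 IC enters a separate analysis: its relationship with progression is estimated and "compared between the atropine and the placebo groups using moderator analysis". The same section justifies this by describing a weak central inner retinal response as a risk factor for myopia development.

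**The concern.** When the question is whether a treatment works alike in two baseline classes, the quantities of interest are the atropine-minus-placebo difference within each class and the contrast between those differences. Their precision depends on how many children fall into each of the four class-by-arm cells. As written, the plan leaves those counts to chance, although the class can be known before allocation.

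The same gap affects the overall comparison of arms. The plan treats the retinal response as prognostic, yet nothing in the described design balances it between arms and nothing in the main GLM adjusts for it. A chance difference in mean Ring 1 IC would pass into the estimated treatment effect in proportion to how strongly Ring 1 IC predicts progression.

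**Working it through.** **The plan's own sample size.** From the means and SDs in the Subjects section:
- Atropine effect: 0.71 / √((0.63² + 0.69²)/2) = 1.07. The protocol's settings are "type I error of 5% and the power of 80%; effect size = 1.07, two-tailed; paired group", and a paired t calculation returns n = 9 (power 80.2%).
- mfERG: 13.57 / √((30.54² + 27.24²)/2) = 0.47, which returns n = 38 (power 80.5%).
- Dropout: 38 / 0.95 = 40, matching "at least 40 subjects aged from 8 to 9 years will be recruited". Two arms give 2 × 40 = 80.

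The figures reproduce, so 80 is used below. The size was built per arm; no class-by-arm cell was planned. Whether a paired formula suits this design is a separate matter.

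**Assumptions.** 40 children per arm, and 40, 24 or 16 fast children among the 80. The documents give neither the ratio nor the fast share, so a range is shown.

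**Check 1: a fast/slow-by-arm contrast.** With F fast children, the number k on atropine is hypergeometric (80, F, 40). The variance of the contrast is proportional to 1/k + 1/(F−k) + 1/(40−k) + 1/(40−F+k). With equal cells it is 4/F + 4/(80−F).

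| Fast children | Equal-cell value | Mean excess if unstratified | 95th percentile: fast-group split | Excess at that split |
|---|---|---|---|---|
| 40 | 0.2000 | 1.3% | 16:24 | 4.2% |
| 24 | 0.2381 | 2.4% | 8:16 | 9.4% |
| 16 | 0.3125 | 4.9% | 5:11 | 13.3% |

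Example, 24 fast children split 8:16: 1/8 + 1/16 + 1/32 + 1/24 = 0.2604, and 0.2604 / 0.2381 = 1.094.

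With 40 fast children, a split of 24:16 or worse has probability 11.7%. That is the same event as the share of fast children differing between arms by 20 percentage points or more (24/40 against 16/40), so it counts once.

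In power terms, for d = 1.07 within a fast group of 40: 90.9% with an exact split and 90.6% averaged over chance splits. With only 20 fast children: 61.9% and 60.2%. For an illustrative 0.71 D difference in effect between classes (SD 0.66 D), interaction power with 40 fast children is 66.0% and 65.4%.

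**Check 2: the SAP's moderator test.** This uses Ring 1 IC, taken here as continuous. The variance of the difference in slopes between arms is proportional to 1/SSx(atropine) + 1/SSx(placebo), where SSx is the within-arm sum of squares of Ring 1 IC. With normal Ring 1 IC and 20,000 simulated allocations, unstratified allocation raises the mean variance over stratified allocation by 0.8%, 1.0% and 1.2% for 40, 24 and 16 fast children. The 95th-percentile variance is higher by 1.1%, 1.1% and 1.5%.

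**Check 3: balance of Ring 1 IC between arms.** Unstratified, the SD of the difference in means is √(1/40 + 1/40) = 0.224, so 95% of absolute differences lie below 1.96 × 0.224 = 0.44 SD. Stratified at a cut with fast share p, the variance 0.05 is multiplied by 1 − φ(z)²/(p(1−p)), where φ is the normal density and z the p-quantile. For p = 0.5, 0.3 and 0.2 the factors are 0.363, 0.424 and 0.510, giving 0.26, 0.29 and 0.31 SD. Simulation gives 0.27, 0.29 and 0.31.

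**The case against.** **The SAP does not analyse four cells.** A reader might infer that the moderator analysis compares atropine effects in a fast and a slow group, so that the 4% to 13% tail in Check 1 applies to it. The SAP does not support that. It has no baseline fast/slow factor. It relates Ring 1 IC itself to progression and compares that relationship between arms, and its only fast progressor is defined by outcome (at least 1.0 D a year), which cannot be a stratification factor. For that analysis the gain is about 1%. This part of the objection stands in full. The four-cell figures apply only to the comparison described in the protocol's Summary.

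**Silence is not a choice.** A reader might infer that simple, unstratified allocation was chosen, perhaps by coin flip, where a group of 40 splits 25:15 or worse with probability 15%. Neither document says so. The documents support only that no method is described and no link to the class is made.

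**The loss is small and the test is unbiased.** Also correct. Chance imbalance does not invalidate the randomised comparison, and the size of the fast group matters more for power than its arm split.

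**Stratifying is not free.** It needs a cut-off that neither document gives. The classifier may also be weak: with normal distributions, equal SDs and equal groups, the pilot effect size of 0.47 implies about 81% overlap and about 59% correct classification at the best cut. Continuous Ring 1 IC as a covariate would deal with imbalance in the main GLM without dichotomising. This is why the fix puts the continuous covariate first. It does not remove the point, because the protocol already commits to classing every child and therefore already needs a cut-off.

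**Conclusion.** The point holds as a modest, inexpensive improvement. The trial's stated question concerns baseline fast and slow classes, randomisation is not tied to them in either document, and the main GLM omits a variable the plan regards as a risk factor.

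The clearest benefit is better balance of Ring 1 IC between arms (95th percentile of the difference about 0.44 SD unstratified, about 0.27–0.31 SD stratified). The precision gain is about 1–5% in variance on average for a fast/slow contrast, and about 1% for the SAP's own moderator test. These figures rest on 80 children, 40:40 arms, a fast share of 50%, 30% or 20% and, for Ring 1 IC, normality.

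A reader might go further and say that the trial is biased, that its moderator test is seriously weakened, or that the remedy costs nothing. The documents and the calculations support none of these.

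**What to change.** In the protocol:
- State the mfERG measure and the cut-off that define fast and slow.
- State that classification is completed before allocation.
- State that children are randomised 1:1 to atropine or placebo in permuted blocks within each class.

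In the SAP: add baseline retinal response to the atropine-versus-placebo GLM, preferably as continuous Ring 1 IC, together with the stratum.

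The cost is two randomisation lists instead of one, a cut-off fixed in advance, and the mfERG read before treatment is assigned. Incomplete blocks may leave a small residual imbalance. No extra children, visits or tests are needed, because the baseline mfERG is already planned for every child.

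The SAP describes delayed follow-up visits in the past tense. If allocation is already complete, the stratification steps no longer apply. In that case, report how allocation was done and the class-by-arm counts, and present the Ring 1 IC-adjusted GLM labelled according to when it was added.

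### The 80% power behind n = 38 is for a marker contrast that the SAP does not test as a mean difference, and it does not carry over to the planned treatment-by-Ring 1 IC moderation

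*Protocol*

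**What the plan says.** The Protocol's Subjects section contains two sample-size calculations. The first, for the effect of atropine on progression, gives 9. The second takes pilot data, "the mean inner retinal responses from fast and slow myopia progression group are 67.04 ± 30.54 uV/deg² and 80.61 ± 27.24 uV/deg²", and concludes "therefore the proposed study requires 38 subjects", on the settings "type I error of 5% and the power of 80%; effect size = 0.47, two-tailed; paired group; GPower 3.1". The larger figure is carried forward: 38 becomes 40 for 5% dropout, and 80 because there are two arms.

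The Protocol's Summary says that the children in this trial "will be allocated into fast or slow myopia progression group in accordance with the electro-retinal activities". It gives as a motive that no clinical finding shows whether fast and slow progressors "will show the same treatment effect of atropine".

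The SAP's Statistical analysis section plans:
- a general linear model of annualized SER and AL change by arm;
- a model relating Ring 1 IC to that change, "compared between the atropine and the placebo groups using moderator analysis";
- a Fisher R-to-Z comparison of the correlations in the two arms;
- an ROC analysis of baseline Ring 1 IC for observed fast progression (at least 1.0 D per year), within each arm.

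It plans no test of mean Ring 1 IC between fast and slow groups. Neither document gives an interaction size or a power for the moderator analysis.

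**The concern.** The calculation that sets the size answers whether the marker differs between fast and slow children. The question that distinguishes this trial is whether the atropine effect differs with the marker. These are different estimands with different standard errors, so power for one says nothing about the other. In addition, the trial's own fast and slow groups are defined by the electro-retinal response, so testing that response between them would be uninformative.

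A reader of the Subjects section could conclude that 80 children are enough to compare the atropine effect across risk groups. If moderation is real but moderate, a non-significant moderator test is the likely result, and it could be taken to mean that fast and slow progressors benefit equally. That matters because the Summary says that the results are meant to guide prescribing.

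**Working it through.** **Inputs from the Protocol, Subjects section.** Progression -0.49 (SD 0.63) D on atropine and -1.20 (SD 0.69) D in control. Marker 67.04 (SD 30.54) in fast and 80.61 (SD 27.24) in slow progressors. Two-sided 5%, power 80%, dropout about 5%, 80 recruited.

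**Assumed, because the documents do not say.** 1:1 allocation; 76 (80 × 0.95) to 80 evaluable children, so 38-40 per arm; residual SD equal to the pooled SD; a normally distributed marker; every interaction size below. Tests are at an unadjusted 5%. Where the SAP's Hochberg adjustment applies, power can only be lower.

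**1. Reproducing the plan's figures.**
- Marker: pooled SD = √((30.54² + 27.24²)/2) = 28.94, and d = 13.57/28.94 = 0.469. A paired t-test at d = 0.47 (noncentrality d√n) has 79.4% power at n = 37 and 80.5% at n = 38. The 38 reproduces.
- Atropine: pooled SD = √((0.63² + 0.69²)/2) = 0.661 D, and d = 0.71/0.661 = 1.07. A paired test has 80.2% power at n = 9. The 9 reproduces.
- 38/0.95 = 40, and 40 × 2 = 80.

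**2. The same contrast with different children in each group.** The 0.47 is a mean difference over a between-child SD, which is a two-sample effect size. The two-sample t-test has noncentrality d√(n/2):

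| Per group | Power at d = 0.47 |
|---|---|
| 19 | 29% |
| 38 | 52% |
| 40 | 55% |
| 73 | 80.5% (the first n above 80%) |

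**3. Atropine versus placebo, unpaired.** At d = 1.07, power is 99.6% with 38 per arm and 99.7% with 40.

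**4. Fisher R-to-Z.** SE = √(2/(n - 3)), which is √(2/35) = 0.239 at 38 per arm and √(2/37) = 0.232 at 40. Converting d = 0.469 to a correlation, assuming an even split: 0.469/√(0.469² + 4) = 0.228 (point-biserial), or 0.228 × 0.5/0.399 = 0.286 (biserial). Take these as the placebo correlation, with zero under atropine:
- r = 0.228: Fisher z 0.232, power 16-17%.
- r = 0.286: Fisher z 0.294, power 23-24%.
- For 80%: a z difference of 2.80 × 0.239 = 0.670 (r = 0.58 versus 0) at 38 per arm, or 2.80 × 0.232 = 0.651 (r = 0.57 versus 0) at 40.

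**5. Moderator analysis with Ring 1 IC continuous, as the SAP describes it.** The SE of the slope difference per marker SD is 0.661 × √(4/N) = 0.152 D at N = 76. Detectable with 80% power: (1.993 + 0.847) × 0.152 = 0.43 D per SD. The halves of a normal marker split at its median have means 2√(2/π) = 1.596 SD apart, so this is about 0.69 D between halves.

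| Difference in atropine effect between marker halves | Power, N = 76 to 80 |
|---|---|
| 0.355 D (half of 0.71) | 30-32% |
| 0.71 D (all of it) | 83-84% |

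**6. If the marker were instead split into two groups.** SE = 0.661 × √(16/76) = 0.303 D. Detectable difference: 2.84 × 0.303 = 0.86 D. Power is 21-22% at 0.355 D and 64-66% at 0.71 D.

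**The case against.** Five points can be made for the plan.

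- **The main comparison is well powered.** Atropine versus placebo comes first in the SAP and has over 99% power on the Protocol's inputs. No primary analysis is named, so moderation as the central question is an inference from the Summary. This stands: the trial as a whole is not shown to be too small.
- **The SAP does contrast the marker between fast and other progressors.** The ROC does so within each arm, with fast progression defined by outcome. At d = 0.47 the AUC would be about 0.63. So a reader who infers that the contrast is wholly absent goes too far. But the ROC is not the mean comparison that was powered.
- **The 38 may not come from a circular contrast.** A reader might infer that it does. The documents support circularity only for the trial's own groups. How the pilot groups were formed is not stated. A median split on a normal marker would give d of about 2.6, so 0.47 does not look like a simple split on that marker.
- **The detectable interaction need not exceed the whole atropine effect.** The 0.86 D figure would suggest that it does, but it belongs to a two-group split. The SAP uses Ring 1 IC undivided, and there the figure is about 0.69 D, slightly below 0.71 D.
- **No interaction size is given.** A flat statement that moderation has 16-24% power is therefore unsupported. That range holds only for Fisher R-to-Z, with the correlation falling from 0.23-0.29 to zero. Larger effects give much higher power.

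None of this supplies a power basis for moderation. Nor does it rescue the paired test: no matching of fast to slow children is described. It is also fair to say that no passage plans to report a non-significant moderator as an equal effect. That is a risk to guard against, not a stated intention.

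**Conclusion.** The concern holds in a limited form. The 38 that leads to 80 is a power figure for a mean contrast that the SAP does not plan. On independent children that contrast has about 52-55% power with 38-40 per group, not 80%; this part rests on the Protocol's own effect size and needs no assumed interaction. The stated 80% cannot be transferred to the moderator analysis or Fisher R-to-Z, whose power is simply not given.

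How weak those tests are depends on the effect assumed. Power is low for modest moderation (16-24% for the Fisher test at the correlations above, 30-32% for the continuous moderator at half the atropine effect) and adequate only for large moderation (83-84% at the full 0.71 D). The SD of 0.66 D is unadjusted, so covariates could improve these figures somewhat. The Protocol does not state the period of its progression figures, whereas the SAP annualizes. Power depends on the ratio of effect to SD, so a common rescaling leaves it unchanged, but the dioptre thresholds would rescale. The documents do not support the stronger conclusion that the study cannot detect moderation.

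**What to change.** **Protocol, Subjects section.**
- Withdraw the 80% claim for the marker contrast, or restate it unpaired: 73 per group for 80%, about 52-55% with 38-40 per group.
- Keep the record of how 80 was reached. The SAP already reports data-dependent results, so the rationale should not be replaced as if it had been different.
- Add, labelled as a later clarification, that 80 gives over 99% power for atropine versus placebo on the Protocol's inputs.

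**Protocol and SAP.** State that moderation was not the basis for the size. Suggested content: with 76 evaluable children, 1:1 allocation and SD 0.66 D, 80% power requires a slope difference of about 0.43 D per SD of Ring 1 IC (about 0.69 D between median halves of a normal marker; 0.86 D if the marker is dichotomised), or for Fisher R-to-Z a correlation of about 0.58 versus 0.

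**SAP, Statistical analysis.** Report the treatment-by-Ring 1 IC interaction as an estimate with a 95% CI. State that a non-significant interaction will not be read as an equal effect in fast and slow progressors.

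**Cost.** Wording only, and no extra children. The price is a weaker claim about moderation.

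### The sample size uses a paired test for comparisons between different children; the fast/slow contrast that sets it has about 52–55% power at best (about 30% within one arm), not 80%

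*Protocol*

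**What the plan says.** The Subjects section of the protocol makes two calculations, each at two-sided 5% and 80% power, and labels both as paired.

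- **Treatment effect.** From a cited earlier trial's progression of −0.49 ± 0.63 D on 0.01% atropine and −1.20 ± 0.69 D in controls, it takes an effect size of 1.07 and concludes that "9 subjects should be required for this project to demonstrate the effect of atropine on myopia control".
- **Fast versus slow.** From pilot inner retinal responses of 67.04 ± 30.54 and 80.61 ± 27.24 uV/deg², it obtains 38 subjects, with "the power of 80%; effect size = 0.47, two-tailed; paired group; GPower 3.1".

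The larger figure is raised for 5% dropout, so that "at least 40 subjects aged from 8 to 9 years will be recruited". The protocol then says: "As this study is a randomized controlled trial with two arms, one is the treatment arm and the other one is placebo arm", and "We will recruit 80 subjects in this study".

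The Summary says that the children "will be allocated into fast or slow myopia progression group in accordance with the electro-retinal activities", and names as an open question "whether the children with either fast or slow myopia progression will show the same treatment effect of atropine". The SAP (Statistical analysis) does not test the fast/slow difference in mean response. It relates Ring 1 IC to annualized change in SER and AL, with the relationship "compared between the atropine and the placebo groups using moderator analysis", and also compares the two arms' correlation coefficients by Fisher's r-to-z test.

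**The concern.** A paired test applies when each observation in one group has a partner in the other, such as the same child twice or a matched pair. Here a child is in the atropine or the placebo arm, and in the fast or the slow group. The documents describe no matching, crossover or fellow-eye control, and give no within-pair correlation or standard deviation of differences. Using a paired test for such groups understates the number needed.

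The 80% therefore does not hold for the contrast that determined the recruited number. The trial's distinctive question is whether atropine works equally in the two kinds of children. The SAP approaches it through the moderator and Fisher z comparisons, for which no power is given. A reader who takes the 80% to cover them could read a non-significant result as evidence of equal effect.

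**Working it through.** **Inputs** (protocol, Subjects): effect sizes 1.07 and 0.47; two-sided 5%; 80% power; 5% dropout; 80 recruited. Equal arms of 40 are implied by the doubling. After 5% dropout, 40 × 0.95 = 38 per arm, or 76 in all.

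**Effect sizes.** Pooled SD = √((s₁² + s₂²)/2).
- Treatment: 0.71 / 0.661 = 1.075.
- Fast/slow: (80.61 − 67.04) / √((30.54² + 27.24²)/2) = 13.57 / 28.94 = 0.469.

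**Reproducing the plan's figures.** For a paired t-test, power comes from the noncentral t with n − 1 degrees of freedom and noncentrality d√n.
- d = 1.07: n = 9 gives 80.2% (n = 8 gives 73.8%).
- d = 0.47: n = 38 gives 80.5% (n = 37 gives 79.4%).
- Dropout: 38 / 0.95 = 40.

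All stated figures match, so the arithmetic is sound and the error is the choice of test. A paired effect size computed with an assumed within-pair correlation of 0.5 would be 0.467 and 1.072, giving the same 38 and 9. With a correlation of 0, the fast/slow contrast would need 74 pairs.

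**Independent groups.** Degrees of freedom are n₁ + n₂ − 2 and noncentrality is d√(n₁n₂/(n₁ + n₂)).
- d = 1.07: 15 per arm gives 80.7% (14 gives 77.8%).
- d = 0.47: 73 per group gives 80.5% (72 gives 79.98%), so 146 evaluable children.

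| Comparison | Groups | Power |
|---|---|---|
| Fast/slow at 0.47, arms pooled, even split | 40 v 40 | 54.6% |
| same, after dropout | 38 v 38 | 52.5% |
| Fast/slow, arms pooled, uneven split | 27 v 53 | 50.1% |
| same | 20 v 60 | 43.6% |
| Fast/slow within one arm | 20 v 20 | 30.5% |
| same, after dropout | 19 v 19 | 29.2% |
| same, uneven split | 10 v 30 | 24.1% |
| Treatment effect at 1.07 | 38 v 38 | 99.6% |
| Treatment effect, the stated 9 read as per arm | 9 v 9 | 56.9% |
| Treatment effect, the stated 9 read as a total | 4 v 5 | 28.2% |

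With arms pooled and an even split, the standardized difference detectable with 80% power is 0.651 (38 v 38) or 0.634 (40 v 40). Multiplied by 28.94, these are 18.8 and 18.4 uV/deg², against a pilot difference of 13.57.

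**Precision of the Fisher z comparison**, before Hochberg's adjustment. SE = √(2/(n − 3)).
- n = 38 per arm: SE = √(2/35) = 0.239; 95% half-width 1.96 × 0.239 = 0.469.
- n = 40 per arm: SE = √(2/37) = 0.232; half-width 0.456.
- If both observed correlations were 0 at 38 per arm, the interval would still include a difference as large as 0 against tanh(0.469) = 0.44.
- Detectable with 80% power at 38 per arm: 2.80 × 0.239 = 0.670 on the z scale, a placebo correlation of about 0.58 against an assumed atropine correlation of 0.

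**Slope-difference (moderator) test.** No single figure can be given. In a simulation with 38 per arm, no covariates and 40,000 runs, at placebo/atropine correlations of 0.58/0, 0.70/0.2 and 0.75/0.3, power was 75%, 68% and 63% with equal outcome variances, but 83%, 89% and 92% with equal residual variances.

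**The case against.** **The 0.47 may not describe the groups to be formed.** The Summary assigns children to fast or slow by their retinal responses. If groups are cut on the response itself, a difference in that response is built in. Under normality, a median split would give a standardized difference of about 2.6. The protocol does not say how the pilot groups were formed. This stands as a condition: the corrected figures are what the protocol's own effect size implies. It does not rescue the paired calculation, and if it applies, the contrast is an even weaker basis for the sample size.

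**Pooling and an even split are assumptions.** True, and they are the favourable ones. Uneven splits lower the power further; after dropout, 25 v 51 gives 47.6% and 19 v 57 gives 41.7%. The within-one-arm reading is less natural for a baseline contrast, for which all children would be used, so about 30% is the pessimistic end.

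**The consequence is limited.** The fast/slow mean contrast is not an SAP analysis, no SAP test is invalidated, and the treatment comparison is well powered. Even within one stratum of 19 v 19, an effect of 1.07 would be detected with about 89% power, although that is not a test of whether the strata differ. All of this stands and confines the error to the stated power and the sizing rationale.

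**The protocol never claims 80% for the moderator or Fisher z tests.** Also true. The risk of misreading is a reason for one clarifying sentence and for intervals, not a second error. The 38 per arm is itself assumed, because the SAP gives no analysed number.

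**Conclusion.** The concern holds. Both sample sizes come from a paired test applied to different children. At the protocol's effect size of 0.47, the contrast that sets the recruited number needs 73 per group, and 80 children give 52–55% power on the favourable assumptions of pooled arms and an even split, falling to about 30% within one arm. No reading of the 80 children examined reaches the stated 80%. The treatment comparison was also wrongly sized (15 per arm, not 9 subjects) but has ample power at the planned size. These figures assume that 0.47 applies to the groups actually formed. The point should be fixed: the error is certain and cheap to correct, but it lies in the sizing statement and not in a planned SAP test.

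**What to change.** 1. In the protocol's sample size text, replace the paired calculations with independent two-sample ones. State 15 per arm for the treatment effect and 73 per group for the fast/slow contrast. Give the power at the planned size as 52–55% with pooled arms and an even split assumed, and about 30% within one arm. Say how the pilot groups behind the 0.47 were formed.
2. State that the 80% does not cover the SAP's Ring 1 IC moderator analysis or the Fisher z comparisons.
3. Report the difference in slopes and the difference in correlations between arms with 95% confidence intervals, so that a non-significant result is not read as equal effect. If a detectable difference is quoted, give it for Fisher z only, with its assumptions (38 per arm, before Hochberg's adjustment, placebo correlation about 0.58 against 0). Do not carry it over to the slope test.

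The cost is wording, added intervals and a less favourable stated power. The SAP is written in the past tense, so this corrects the record and asks for no further recruitment. The treatment comparison does not change.
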